4.4 Early Withdrawal of Subjects

4.4.1 When and How to Withdraw Subjects

Subjects have the right to withdraw from the study at any time, for any reason, and without repercussion. The investigator, [name], has the right to withdraw a patient from the study in the event of an intercurrent illness, adverse event (AE), treatment failure, protocol violation, and for administrative or other reasons. An excessive rate of withdrawals would reduce the amount of data available for analysis and limit the ability to interpret the study results; therefore, unnecessary withdrawal of patients should be avoided.

If subjects become pregnant during the study, then their participation will be stopped.

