4.4.3 Data Collection and Follow-up for Withdrawn Subjects

Patients who withdraw prematurely from the study may be asked to complete an end of study visit per the study procedures. In addition, any ongoing adverse drug reactions or study-related adverse events will be followed until resolution or documentation of why there will be no resolution if the event will be ongoing.

5 Study Procedures

| Procedure | Screening Visit | Day 1 Visit | 6 Week Follow-Up Visit (+/- 7 days) |
|---|------------------|----------------|-------------------------------------|
| Eligibility Review | X | | |
| Informed Consent | X | | |
| Demographics | X | | |
| Medical History | X | | |
| Current Medications | X | X | |
| Vital Signs | X | | X |
| Questionnaires | X | | X |
| Research blood collection | X ¹ | | X |
| EGD with EREF and biopsies | X ^{1,2} | | X ² |
| Adverse Events | X | X | X |
| Dysphagia Symptom Questionnaire (DSQ) | | X ³ | X ³ |
| Nutrition Counseling | | X ² | |
| Allergy Skin Testing | | X ⁴ | |
| Diet Elimination | | X ⁵ | |

¹ Subjects must be scheduled for a routine care EGD with biopsies (clinical and research) at UNC or have had a routine care EGD with clinical and research biopsies at UNC within 3 months prior to enrollment. If subjects have had a recent EGD as defined above, then results from clinical biopsies taken during that EGD will be used to assess eligibility for this study, and research biopsies and EREFs from that EGD will also be used for this study. In these cases, an additional EGD does not need to be performed. In addition, if research blood was collected during the recent EGD and can be used in this study, then subjects will have an abbreviated blood collection during the screening visit. If subjects have not had an EGD with research and clinical biopsies at UNC within 3 months of enrollment, then they must be scheduled to receive a routine care EGD with biopsies at UNC during which clinical and research biopsies will be collected for this study.

² These procedures are considered routine care and are billed to the subject and/or subject's insurance.

³ The DSQ is started 2 weeks prior to the Day 1 and 6 week visits.

⁴ Results from the allergy skin testing will not be used to drive the food elimination diet.

⁵ Subjects will begin diet elimination on day 1 and continue for 6 weeks.

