6.2 Statistical Methods

To determine the response rate for the primary outcome, the number of subjects with <15 eos/hpf on follow-up endoscopy will be calculated. For secondary outcomes, median eosinophil counts, endoscopy scores, and symptoms scores will be compared before and after treatment with Wilcoxon signed-rank. These will be contextualized by calculating odds ratios and 95% confidence intervals where appropriate, so as not to

over-rely on p values alone. Patients who drop out or who have incomplete data for the outcomes will be excluded from analysis. Because this study's outcomes are determined after the treatment period and follow-up endoscopy, a subject must complete this end of treatment evaluation for us to be able to include their data in the analysis. We do not feel that selection bias would impact the analysis if there are incomplete data due to drop out. We are not performing a comparative analysis between groups, so drop out would not be dependent on different treatments administered in different study arms. In addition, in our experience with previous clinical studies of EoE, dropout rates have been quite low.

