8.3 Case Report Forms

The study will utilize paper case report forms (eCRFs). All data requested on the CRF must be recorded. All missing data must be explained in the comments section of the CRF. Data will then be entered into a secure Excel workbook.

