9.1 Study Monitoring Plan

This study will be monitored regularly by a study monitor who is not directly involved in the project to ensure accurate data entry and reporting, as well as compliance with all applicable federal regulations. Refer to the most recent study monitoring plan for additional details.

The monitor is responsible for ensuring:

- (a) the rights and well-being of trial participants are protected,
- (b) reported trial data are accurate, complete, and verifiable from source documents,
- (c) the conduct of the trial is in compliance with the currently approved protocol/amendments, with GCP, and with the applicable regulatory requirements, and data reported are verifiable to support meeting the study objectives.

Procedures and sources of information:

- A) Protection of the rights and well-being of study subjects by verifying:
 1. Investigator(s) have adequate qualifications, education and training, and resources necessary to conduct the study.
 2. Verify the investigator and his staff follow the approved protocol and all approved amendments, if any
 3. The investigator personally conducts or adequately supervises his study staff
 4. Study staff are adequately trained and study functions are delegated to authorized individuals
 5. Written informed consent was obtained before each subject's participation in the study
 6. Enrollment of only eligible subjects

7. Subjects are instructed in the proper use, storage and return of the investigational product
8. Adequate and accurate case histories that record all observations are maintained
9. Unanticipated adverse events are reported in accordance with the protocol
- B) Trial data are accurate, complete and verifiable from source documents as verified from review of subject file, case report forms, and medical procedures reports
 1. Verify that the investigative staff are performing the specific trial functions in accordance with the protocol
 2. Checking the accuracy and completeness of case report form entries, source documents and other trial related records against each other
 3. Adequate and accurate case histories that record all observations are maintained
 4. All withdrawals and dropouts are properly reported and explained
 5. Investigator is informed of protocol deviations, data entry errors and omissions and illegibility
- C) Study is conducted in compliance with the currently approved protocol/amendments, with GCP, and applicable regulatory requirements

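### The primary response rate is taken among completers only, and the reason given for ruling out selection bias does not apply to a single proportion

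*Combined protocol and SAP*

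**What the plan says.** Section 3.4 defines the primary outcome as a post-treatment count below 15 eos/hpf. On who is analysed, the Study Summary and sections 6.2 and 6.3 agree: "Patients who drop out or who have incomplete data for the outcomes will be excluded from analysis". Section 6.2 adds that "a subject must complete this end of treatment evaluation for us to be able to include their data in the analysis". Section 6.3 contains nothing beyond the exclusion, and no imputation rule or sensitivity analysis appears anywhere.

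Section 6.2 gives two reasons why this is acceptable. The first is that no comparison between groups is made, from which it concludes: "We do not feel that selection bias would impact the analysis if there are incomplete data due to drop out". The second is that "in our experience with previous clinical studies of EoE, dropout rates have been quite low", without a figure.

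On how subjects leave, section 4.4.1 says the investigator "has the right to withdraw a patient from the study in the event of an intercurrent illness, adverse event (AE), treatment failure, protocol violation", as well as for administrative or other reasons. The same section stops participation on pregnancy and asks that unnecessary withdrawals be avoided. Section 4.4.3 says: "Patients who withdraw prematurely from the study may be asked to complete an end of study visit per the study procedures".

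Reasons for loss will be on file. Section 8.3 requires that "All missing data must be explained in the comments section of the CRF", and among the items the monitor verifies under section 9.1 is "All withdrawals and dropouts are properly reported and explained". The statistical plan makes no use of this information.

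**The concern.** A subject who starts the assigned diet and has no follow-up biopsy disappears from the denominator. Section 2 sets out to evaluate the effectiveness of the diet strategy and states its hypothesis for patients with active EoE, not for those who complete. Abandoning the diet is one way such a strategy can fail, and section 1.1 itself links compliance to response. If losses are related to response, the completer rate describes a selected group.

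Section 6.1 says the response rates will feed directly into a grant application for a randomized study. A completer rate reported alone would not show how far it depends on who was lost.

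Two points of wording add to this. The text does not settle whether a withdrawn subject who does have follow-up histology is analysed. And because the exclusion refers to outcomes in the plural, a subject with a biopsy result but a missing symptom diary (DSQ) or endoscopy score could be read as excluded from the histology analysis too.

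**Working it through.** **Inputs.** Section 6.1 gives 20 completers and 15 responders. The number lost after Day 1, *d*, and the response rate among lost subjects, *r*, are not given. Both are assumptions here: *d* = 1, 2 or 3, and *r* = 0, 50 or 100%.

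**The plan's own figure.** 15/20 = 75.0%, as stated. The exact (Clopper-Pearson) 95% interval is 50.9 to 91.3%. The 47 to 92% in section 6.1 was not reproduced by the exact, Wilson (53.1 to 88.8%) or Wald (56.0 to 94.0%) method. That is a separate matter and nothing below depends on it.

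**Bias of the completer rate.** Let *p* be the response rate in completers. The rate among all who start the diet is (20*p* + *d r*)/(20 + *d*). Subtracting this from *p* gives

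bias = [*d*/(20 + *d*)] × (*p* − *r*).

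It is positive if *r* < *p*, zero if *r* = *p* and negative if *r* > *p*. No term involves a comparison group, so the absence of one cannot make the bias zero.

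**With *p* = 0.75:**

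| *d* | Lost counted as non-responders (exact 95% CI) | Overstatement, *r* = 0 | Overstatement, *r* = 50% | Rate if all lost had responded |
|---|---|---|---|---|
| 1 | 15/21 = 71.4% (47.8 to 88.7) | 1/21 × 0.75 = 3.6 points | 1/21 × 0.25 = 1.2 points | 16/21 = 76.2% |
| 2 | 15/22 = 68.2% (45.1 to 86.1) | 2/22 × 0.75 = 6.8 points | 2/22 × 0.25 = 2.3 points | 17/22 = 77.3% |
| 3 | 15/23 = 65.2% (42.7 to 83.6) | 3/23 × 0.75 = 9.8 points | 3/23 × 0.25 = 3.3 points | 18/23 = 78.3% |

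**Is the asymmetry informative?** No. Larger falls than rises follow from starting at 75%. At 10/20 the ranges are symmetric about 50%: 47.6 to 52.4%, 45.5 to 54.5% and 43.5 to 56.5% for one, two and three losses.

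**Position relative to 75%.** The planned 15/20 sits exactly on the hypothesised minimum, so at that result one loss counted as a non-response takes the estimate below it. No test or decision rule is attached to 75%, so this affects description only.

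**The case against.** The best defence is that this is an openly described proof-of-principle pilot whose stated target is 20 completing subjects, and that response following treatment is a legitimate quantity for it. The direction of any bias is not established. Section 1.1 ties compliance to response but says nothing about dropout. Some losses may be unrelated to response: pregnancy, administrative withdrawal, or cost, since the week-6 EGD is routine care billed to the subject or insurer (section 5, table note 2). Counting all of these as failures replaces one untestable assumption with another. With dropout as low as the plan expects, the effect is a few points inside an interval about 40 points wide.

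Most of that stands, and it limits the point to a conditional one of modest size. It does not rescue the stated justification, which is wrong for a single proportion however few subjects leave, and it does not explain why no sensitivity analysis is planned.

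Two stronger readings are tempting. A reader might infer that withdrawal for treatment failure lets histologic non-responders be removed before they count. The documents do not support that: no endoscopy is scheduled between Day 1 and week 6, so such a withdrawal would have to rest on something other than scheduled histology. A non-adherent subject who attends the week-6 EGD also stays in and can lower the completer rate. A reader might also take the gap between 30 enrolled and 20 completing as expected dropout, giving 15/30 = 50.0%. But sections 3.1 and 5.1.2 place screen failures after consent in that gap, and those subjects never start the diet.

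**Conclusion.** The concern holds in conditional form. The plan reports a completer rate with no companion analysis, and its main reason for dismissing selection bias does not bear on a single-arm rate. The completer rate is too high only if lost subjects respond less often than completers. That is plausible for losses through treatment failure, adverse events or abandoning the diet. It is not shown, and it need not hold for pregnancy, administrative or cost-related losses. It would be wrong to conclude that the reported rate will be inflated.

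For one to three assumed losses at 15/20, the overstatement runs from 1.2 to 3.3 points if lost subjects respond at 50%, and from 3.6 to 9.8 points if none respond. It vanishes if they respond at 75%. The change is worth making because the rate will inform a later trial and the remedy uses data already collected. It is not a threat to the study's validity.

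**What to change.** In the Study Summary and sections 6.2 and 6.3:

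- Define the analysis set as all subjects with confirmed active EoE who start the assigned diet on Day 1. Screen failures stay excluded.
- Use every available follow-up EGD histology result. This includes results from withdrawn subjects where authorization allows (section 8.1) and results from EGDs outside the ±7 day visit window. Flag the latter and add a within-window sensitivity analysis. The window in sections 5 and 5.3 is a visit window, so an observed late response should not be turned into a non-response.
- Count as non-responders only subjects with no follow-up histology.
- Report this rate together with the completer rate, the number lost and the recorded reason for each.
- State that missing DSQ or endoscopy score data affect only that secondary outcome.
- Delete the statement that selection bias would not affect the analysis.

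The cost is a change of wording, with no new visits or data. The rate may come out somewhat lower, and it is conservative for losses unrelated to response. The completer rate beside it makes that visible.

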6.3 Subject Population(s) for Analysis

Patients who drop out or who have incomplete data for the outcomes will be excluded from analysis

7 Safety and Adverse Events

7.1 Definitions

Unanticipated Problems Involving Risk to Subjects or Others (UPIRSOs)

Any incident, experience, or outcome that meets all of the following criteria:

- Unexpected in nature, severity, or frequency (i.e. not described in study-related documents such as the IRB-approved protocol or consent form, the investigators brochure, etc)
- Related or possibly related to participation in the research (i.e. possibly related means there is a reasonable possibility that the incident experience, or outcome may have been caused by the procedures involved in the research,
- Suggests that the research places subjects or others at a greater risk of harm (including physical, psychological, economic, or social harm) than was previously known or recognized.

Adverse Event

An **adverse event** (AE) is any untoward or unfavorable medical occurrence in a human subject, including any abnormal sign (for example, abnormal physical exam or laboratory finding), symptom, experience, or disease, temporally associated with the subject's participation in the research, whether or not considered related to the subject's participation in the research. Adverse events encompass both physical and psychological harms. Intercurrent illnesses or injuries should be regarded as adverse events. Abnormal results of diagnostic procedures are considered to be adverse events if the abnormality:

- results in study withdrawal
- is associated with a serious adverse event
- is associated with clinical signs or symptoms
- leads to additional treatment or to further diagnostic tests
- is considered by the investigator to be of clinical significance

Serious Adverse Event

Adverse events are classified as serious or non-serious. A **serious adverse event** is any AE that is:

- fatal
- life-threatening
- requires or prolongs hospital stay
- results in persistent or significant disability or incapacity
- a congenital anomaly or birth defect
- an important medical event

Important medical events are those that may not be immediately life threatening, but are clearly of major clinical significance. They may jeopardize the subject, and may require intervention to prevent one of the other serious outcomes noted above. For example, drug overdose or abuse, a seizure that did not result in in-patient hospitalization, or intensive treatment of bronchospasm in an emergency department would typically be considered serious.

All adverse events that do not meet any of the criteria for serious should be regarded as ***non-serious adverse events***.

Serious vs. Severe

The term "severe" is often used to describe the intensity (severity) of a specific event (as in mild, moderate, or severe); the event itself, however, may be of relatively minor medical significance (such as severe headache). This is not the same as "serious," which is based on patient/event outcome or action criteria usually associated with events that pose a threat to a patient's life or functioning. Seriousness (not severity) serves as a guide for defining regulatory reporting obligations.

Unanticipated Adverse Device Effect

Any serious adverse effect on health or safety or any life-threatening problem or death caused by, or associated with, a device, if that effect, problem, or death was not previously identified in nature, severity, or degree of incidence in the investigational plan or application (including a supplementary plan or application), or any other unanticipated serious problem associated with a device that relates to the rights, safety, or welfare of subjects (231CFR812.3(s)).

Adverse Event Reporting Period

The study period during which adverse events must be reported is normally defined as the period from the initiation of any study procedures to the end of the study treatment follow-up. For this study, the study treatment follow-up is defined as 30 days following the last administration of study treatment.

Preexisting Condition

A preexisting condition is one that is present at the start of the study. A preexisting condition should be recorded as an adverse event if the frequency, intensity, or the character of the condition worsens during the study period.

General Physical Examination Findings

At screening, any clinically significant abnormality should be recorded as a preexisting condition. At the end of the study, any new clinically significant findings/abnormalities that meet the definition of an adverse event must also be recorded and documented as an adverse event.

Post-study Adverse Event

All unresolved adverse events should be followed by the investigator until the events are resolved, the subject is lost to follow-up, or the adverse event is otherwise explained. At the last scheduled visit, the investigator should instruct each subject to report any subsequent event(s) that the subject, or the subject's personal physician, believes might reasonably be related to participation in this study. The investigator should notify the study sponsor of any death or adverse event occurring at any time after a subject has discontinued or terminated study participation that may reasonably be related to this study. The sponsor should also be notified if the investigator should become aware of the development of cancer or of a congenital anomaly in a subsequently conceived offspring of a subject that has participated in this study.

Abnormal Laboratory Values

A clinical laboratory abnormality should be documented as an adverse event if any one of the following conditions is met:

- The laboratory abnormality is not otherwise refuted by a repeat test to confirm the abnormality
- The abnormality suggests a disease and/or organ toxicity
- The abnormality is of a degree that requires active management; e.g. change of dose, discontinuation of the drug, more frequent follow-up assessments, further diagnostic investigation, etc.

Hospitalization, Prolonged Hospitalization or Surgery

Any adverse event that results in hospitalization or prolonged hospitalization should be documented and reported as a serious adverse event unless specifically instructed otherwise in this protocol. Any condition responsible for surgery should be documented as an adverse event if the condition meets the criteria for an adverse event.

Neither the condition, hospitalization, prolonged hospitalization, nor surgery are reported as an adverse event in the following circumstances:

- Hospitalization or prolonged hospitalization for diagnostic or elective surgical procedures for a preexisting condition. Surgery should **not** be reported as an outcome of an adverse event if the purpose of the surgery was elective or diagnostic and the outcome was uneventful.
- Hospitalization or prolonged hospitalization required to allow efficacy measurement for the study.
- Hospitalization or prolonged hospitalization for therapy of the target disease of the study, unless it is a worsening or increase in frequency of hospital admissions as judged by the clinical investigator.

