1.1 Background

Over the past decade, eosinophilic esophagitis (EoE) has rapidly increased in incidence and prevalence, becoming a major cause of chronic gastrointestinal morbidity. EoE is defined by pathologic infiltration of eosinophils into the esophageal mucosa, leading to dysphagia and progressive esophageal stenosis, and is now the most common cause of food impaction in the U.S. EoE is a chronic, allergic/immune-mediated condition that appears to be driven primarily by IL-5+ and IL-13+ T cell responses to food antigens, based on studies observing disease remission in individuals empirically avoiding all potentially allergenic foods. However, such radical elimination diets are not feasible and there is no currently available test to accurately identify specific food triggers in EoE. Because of this, successful dietary therapy requires empiric elimination of a large number of foods, subsequent reintroduction of single foods, and invasive monitoring (endoscopy with biopsy) to assess response. There is a critical need to develop methods to reliably identify allergen triggers.

In Phase I of the Team Translational Science Award, we began to address these key knowledge gaps. Using prospectively collected biospecimens, we successfully developed a novel T cell directed approach whereby allergen-specific T cells were correlated with known dietary triggers of EoE. We examined esophageal tissue, duodenal tissue, and blood, and found that the blood compartment was the most reliable for extracting, culturing, and stimulating T cells. This demonstration was the first time in humans with EoE that potential food triggers could be detected with a T cell signature in the blood, and it provided proof-of-principle of a clinical application of individualized food elimination regimens. We also performed preliminary studies detecting allergen-specific IgG4 in esophageal biopsies, a recently described pathogenic mechanism of EoE. We feel that the combination of these techniques will allow determination of allergen-specific immune signatures in EoE patients. These hold great promise to impact clinical practice by accurately identifying foods to eliminate in dietary therapy, thus increasing compliance and ultimately response rates. However, additional steps are required before clinical adoption of this approach.

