7.2 Recording of Adverse Events

At each contact with the subject, the investigator must seek information on adverse events by specific questioning and, as appropriate, by examination. Information on all adverse events should be recorded immediately in the source document, and also in the appropriate adverse event module of the case report form (CRF). All clearly related signs, symptoms, and abnormal diagnostic procedures results should be recorded in the source document, though should be grouped under one diagnosis.

All adverse events occurring during the study period must be recorded. The clinical course of each event should be followed until resolution, stabilization, or until it has been determined that the study treatment or participation is not the cause. Serious adverse events that are still ongoing at the end of the study period must be followed up to determine the final outcome. Any serious adverse event that occurs after the study period and is considered to be possibly related to the study treatment or study participation should be recorded and reported immediately.

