7.3.2 Notifying the FDA – Unanticipated Adverse Device Effects

Unanticipated adverse device effect means any serious adverse effect on health or safety or any life-threatening problem or death caused by, or associated with, a device, if that effect, problem, or death was not previously identified in nature, severity, or degree of incidence in the investigational plan or application (including a supplementary plan or application), or any other unanticipated serious problem associated with a device that relates to the rights, safety, or welfare of subjects (21CFR812.3(s)).

Per 21CFR812.46(b) the sponsor ([name]) shall immediately conduct an evaluation of any unanticipated adverse device effect.

A sponsor who determines that an unanticipated adverse device effect presents an unreasonable risk to subjects shall terminate all investigations or parts of investigations presenting that risk as soon as possible. Termination shall occur not later than 5 working days after the sponsor makes this determination and not later than 15 working days after the sponsor first received notice of the effect

Per 21CFR812.150(b), a sponsor ([name]) who conducts an evaluation of an unanticipated adverse device effect under §812.46(b) shall report the results of such evaluation to FDA and to all reviewing IRB's and participating investigators within 10 working days after the sponsor first receives notice of the effect. Thereafter the sponsor shall submit such additional reports concerning the effect as FDA requests.

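### Section 7.1 leaves EoE admissions out of adverse event reporting unless the investigator judges them worse or more frequent, and gives no criterion for that judgment

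*Combined protocol and SAP*

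**What the plan says.** Under its subheading on hospitalization and surgery, Section 7.1 first makes any AE that leads to hospitalization a serious AE, unless the protocol instructs otherwise. It then gives such an instruction: "Neither the condition, hospitalization, prolonged hospitalization, nor surgery are reported as an adverse event in the following circumstances". The third circumstance listed is "Hospitalization or prolonged hospitalization for therapy of the target disease of the study, unless it is a worsening or increase in frequency" of admissions; the qualifier in full is "unless it is a worsening or increase in frequency of hospital admissions as judged by the clinical investigator".

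Four other provisions bear on how far this reaches:

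- Section 7.1, preexisting conditions: a condition present at the start of the study "should be recorded as an adverse event if the frequency, intensity, or the character of the condition worsens during the study period".
- Section 7.2: "All adverse events occurring during the study period must be recorded".
- Sections 7.1 and 7.3.2: an unanticipated adverse device effect includes "any serious adverse effect on health or safety or any life-threatening problem or death caused by, or associated with, a device", if not previously identified in the plan. Section 3.2 separately requires records of device effects, whether anticipated or not.
- Sections 7.1 and 7.3.1.1: an unanticipated problem involving risk to subjects or others has its own three criteria and need not be an AE.

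Section 3.2 identifies the device as the algorithm that diagnoses food allergens. Under Section 5.2, subjects remove one to five foods according to the assay results.

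**The concern.** Excluding target-disease admissions makes sense where such admissions are background noise. Here they are also a way in which device failure could show itself. If the algorithm misses a trigger, the subject keeps eating it and EoE can stay active. Section 1.1 says that EoE leads to dysphagia and progressive stenosis and "is now the most common cause of food impaction in the U.S".

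The exclusion covers the condition as well as the stay, so an excluded event is not merely downgraded from serious to non-serious. It leaves AE reporting altogether.

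Little else in the plan would pick it up. The outcomes in Section 3.4 are eosinophil count, endoscopy score and symptom score, and none counts admissions. A subject withdrawn for treatment failure (Section 4.4.1) who does not complete the follow-up endoscopy is also left out of the efficacy analysis (Section 6.3). At stake is the completeness of the serious AE record of a small trial of an investigational device.

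**Working it through.** The protocol states no figure to reproduce, and no formula decides the point. The check is to read the provisions together and follow an EoE admission through them.

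**Time available for the judgment.** The diet lasts 6 weeks and the follow-up visit window is plus or minus 7 days (Section 5): 42 − 7 = 35 days to 42 + 7 = 49 days. Section 7.1 extends AE reporting to 30 days after the last study treatment. If the diet is taken as the study treatment (my assumption, since the sentence speaks of administration), the period from Day 1 is 35 + 30 = 65 to 49 + 30 = 79 days.

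**Case A: an admission judged to be a worsening or part of an increase in frequency.** The qualifier removes it from the exclusion. It is an AE, it is serious because of the hospitalization, and it can be assessed as a device effect. The preexisting-condition rule points the same way. A first impaction in a subject with none before would ordinarily fall here.

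**Case B: an admission judged to be neither.** Take a subject with earlier impaction admissions who is admitted again while on a diet that missed a trigger. A missed trigger may produce persistence rather than deterioration, so the investigator can reasonably call the disease unchanged. The qualifier is then not met, the preexisting-condition rule is not met, and neither the condition nor the stay is reported as an AE.

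**How well A and B can be told apart.** The item does not define worsening. It sets no reference period for admission frequency, and one admission in 35 to 49 days says little about whether a rate has risen. The preexisting-condition rule does supply a reference point, the start of the study, but no measure of change. The judgment belongs to the investigator. Under Section 7.5 the site principal investigator also determines severity and causality, and Section 3.2 shows that this is a sponsor-investigator trial. Two similar admissions could be classified differently with nothing in the text to settle the matter.

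**What follows for a Case B event.** Section 7.2 routes AEs to the AE module of the case report form, and Section 7.5 has individual AEs reviewed weekly. The only safety-capture item in the visit schedule is the AE row, and no separate device-effect form is described. The device-effect and unanticipated-problem duties remain in force, but the ordinary route by which someone would notice the event is missing.

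**The case against.** The strongest reply is that the qualifier and the preexisting-condition rule together bring back most true deterioration, which is what one would most want recorded. That stands, and it leaves only Case B.

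A reader might infer more from the wording than it supports:

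- **That EoE admissions are exempt outright.** They are not; the qualifier is part of the same item.
- **That such events escape device-effect evaluation or unanticipated-problem reporting.** Neither definition refers to the AE exclusion, and Section 7.3.1.1 says expressly that an unanticipated problem may not be an AE. Only the AE and serious AE route is affected; the loss elsewhere is a lower practical chance of being noticed.
- **That Section 7.1 contradicts Section 7.2.** Section 7.1 settles what is reported as an AE, and Section 7.2 then requires AEs to be recorded. That is a carve-out, not a conflict.
- **That emergency visits without admission, or outpatient dilations, are lost too.** The item concerns hospital stays. These events remain under the general AE definition.
- **That this is the main harm of a wrong diet.** The documents do not rank such harms. They support only that it is foreseeable.

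**Conclusion.** The point holds in its narrow form. An EoE admission during the diet that the investigator regards as neither worse nor more frequent than before would be absent from the AE and serious AE record. The text gives no basis for making that call consistently over about 6 weeks.

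Its size cannot be stated, because the documents give no admission or impaction rate. Two figures are tempting substitutes. At the 75% response target, 0.25 × 20 = 5 completers would be histologic non-responders. From Table 4, 1 − 0.64 = 36% of milk triggers would be missed at face value. Neither is an admission rate, and neither should be used as one. For scale only, one hypothetical unrecorded event would be 1/20 = 5% of the completers aimed for, or 1/30 = 3.3% of the maximum enrolled.

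Nor does the protocol say that the later randomized study will rest on serious event counts; Section 6.1 mentions response rates and magnitude of response. The primary outcome is not affected. The conclusion assumes that some subjects enter with earlier EoE admissions, which the eligibility criteria permit but do not quantify. I would class the change as a cheap improvement.

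**What to change.** Delete the third item of the exclusion list in Section 7.1, or limit it to elective EoE admissions planned before enrollment. Add a sentence stating that every unplanned admission for EoE, food impaction included, within the AE reporting period is recorded as an AE, is classed as serious if it meets the Section 7.1 list, and is checked against the device-effect definition in Section 7.3.2. The sentence should say that it takes precedence over the rest of the exclusion list, because the first item also exempts stays for diagnostic or elective surgical procedures for a preexisting condition.

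The cost is one wording change and a prompt on the case report form. A few background-disease events will be recorded that would otherwise have been left out; the causality assessment already in Section 7.5 can deal with them. Only recording changes, not clinical care.
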